### **2.1.2 Phase 2 observational study**

- To describe pseudonymised data on paediatric and adolescent patients with mpox infection in terms of presentation, clinical course, and outcomes. Depending on the numbers reported, this may include:
  - a) monitoring the temporal and geographical spread of cases of mpox infection in the paediatric and adolescent population, including in specific paediatric groups, such as those with underlying conditions;
  - b) describing the epidemiology and clinical presentation of the infection, including outcomes of treatment administered as part of routine care;
  - c) describing the populations at highest risk of severe outcomes, including identifying factors associated with severe disease and death;
  - d) among mpox patients who are pregnant, describing the infection status of offspring (and estimating vertical transmission risk, if feasible), and characteristics and outcomes of infants with vertically acquired mpox infection.

The Phase 2 consented study will allow collection of pseudonymised data allowing more detailed analyses than are possible in Phase 1 (unconsented and anonymised).

### **2.1.3 Phase 3 nested sub studies**

Each nested sub study implemented in Phase 3 will have its own objectives and protocol.

### **3 STUDY DESIGN**

#### **3.1 DESIGN**

This is a multicentre, observational study on mpox in infants, children and adolescents which involves European and non-European countries.

The study includes three phases (described above), of which this protocol describes Phases 1 and 2.

##### **Phase 1 registry.**

An online registry will be developed to collect anonymised routine clinical data on patients with laboratory confirmed mpox infection aged <18 years. This may include pregnancy and neonatal data both for adolescents who are pregnant or up to 28 days postnatal and have mpox, and infants diagnosed with mpox in the neonatal period. Because all data collected will be fully anonymised, ethics approval may not be required in some or all countries, allowing swift implementation of the registry in response to an outbreak.

Data to be collected include clinical characteristics, symptoms and disease severity, treatments received and outcomes. Data for each patient will be reported at a single point in time, at the end of the clinical episode (e.g. at discharge from care). Data will be collected on historic cases (occurring before the inception of the registry), and on incident cases where relevant approvals and/or consent have not been obtained for Phase 2. Only routinely collected clinical data will be reported.

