##### **Phase 2 observational study.**

When Phase 2 is activated, it will be implemented at each participating site when all required approvals are in place. Phase 2 consists of the development of a prospective observational study which will collect the same data as for the Phase 1 registry, as well as additional data such as dates of events and date of birth which are considered pseudonymised data. For this reason, informed consent/assent will be required from participants and/or their legal guardian. Patients (and/or their legal guardian) may be asked for permission to link their data to other medical records, and to be contacted for further research studies.

If the patient/legal representative does not give consent to participate in Phase 2, the study team will proceed with entering data only into the Phase 1 anonymous registry database.

The eCRF will be based on routine patient visits, and all visits from initial presentation (diagnosis or admission) onwards (follow-up visits) will be entered, until the infant, child or adolescent is considered fully discharged from care (outcome visit). Follow-up of infants born to adolescent mothers who acquired mpox in pregnancy to ascertain neonatal outcomes should end at or before day 28 after the baby is born. If consent is sought for collecting detailed information on infants who acquired mpox and whose mothers are already recruited in the study, linkage of maternal study ID and infant study ID will be made (see section 6.1 for more details).

Only routinely collected clinical data will be entered in the database.

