## 5 STUDY PROCEDURES AND SITES

For Phases 1 and 2, there will be no change to patient care as a result of inclusion in the study; data will be collected on clinical status, treatments received, and outcomes as recorded in routine care and not according to a defined schedule of procedures.

**Phase 1** will collect basic, routine and anonymised data. Where required, each site will be responsible for seeking the country-appropriate ethics approvals or waivers, and it is expected that most will be granted waivers or provide evidence that approval is not required. The link to the online data capture system will be shared through existing networks of clinicians and researchers working in related areas, with an invitation to enter details on all cases of mpox infection aged <18 years seen in their centres. This will include retrospective entry of cases seen before activation of the data entry system as well as incident cases, where approvals are not yet in place for Phase 2, or participants have not consented to Phase 2. Summary data will be entered at the end of each patient's clinical episode.

Patients already entered into the Phase 1 database will not be contacted to give their consent to join Phase 2, to avoid duplication.

For **Phase 2**, patients and (where appropriate) their legal guardians will be informed about the study and asked for consent / assent to take part (see further details in Section 8.3: Informed Consent). Consent can be sought at any point from first presentation (at diagnosis or admission) of the patient until discharge from care. Where consent is given, the 'Initial Presentation Form' in REDCap should be completed as soon as possible and thereafter, each site can decide to perform the data entry following each patient visit or at the point of patient discharge from care. Longer term follow-up or enhanced data collection may be enabled through linkage to routine data sources (e.g. hospital and primary care records), if additional consent is granted.

Where consent is not given for Phase 2, anonymised data will be entered as in Phase 1 (if permitted under local ethics requirements).

Specific study procedure relevant to **Phase 3** will be detailed in the appropriate sub study protocol.

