## 6 DATA MANAGEMENT

### 6.1 REDCAP

Source documents are represented by documents where data are first recorded, and from which participants' electronic case report forms (eCRF) data are obtained. These include, but are not limited to, hospital records (from which medical history and previous and concurrent medication may be summarised into the CRF).

In this study, primary data sources are collected in eCRFs completed by study staff at participating sites. Source data will be collected directly into a web-based REDCap database specifically designed by the study team. A separate but interoperable REDCap database will be developed for each phase: 1) the unconsented, anonymised data, 2) consented, pseudonymised data, and 3) each additional sub study initiated in Phase 3 (each to be described in its own protocol).

To enhance accuracy, data will be subjected to logic and consistency checks, e.g., for implausible values and inconsistencies. Potential errors will be investigated and discussed between the data manager, statisticians, and individual sites.

In Phase 1, data for each patient will be entered at the end of clinical follow-up and each clinical site will transcribe into the eCRF only anonymous retrospective data from source data. No personal identifiable data will be entered into the eCRF (e.g., date of birth will be replaced with age group at diagnosis).

[figure not shown]
In Phase 2, pseudonymised data will be collected. The 'Initial Presentation Form' in REDCap should be completed as soon as possible and thereafter, each site can decide to perform the data entry following each patient visit or as in Phase 1, at the point of patient discharge from care.

In Phase 1 data will be fully anonymous therefore no identifiers will be recorded, whereas in Phase 2 the participants will be identified by a unique study-specific number and/or code in any database. The name and any other identifying detail will be retained only by the site staff on the consent form and the clinical records.

Phase 2 maternal-infant record linkage: If consent is sought for collecting detailed information on an infant with mpox whose adolescent mother has mpox and is already recruited in the study, the mother's study ID should be reported by the study staff on the newly generated infant record, to allow for linkage of maternal study ID and infant study ID.

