### **8.3 INFORMED CONSENT**

Written informed consent to enter into the Phase 2 study must be obtained from parent/legal guardian before any data are entered into the database; children / adolescents may also consent themselves without legal guardian consent where this is permitted under national regulations. Children deemed able to understand the study should give assent according to national regulations/guidelines, those who do not assent must not be included in the study. A specific consent will be sought from mothers of infants diagnosed with mpox at 28 days of life or less, to collect pregnancy and delivery data relating to the birth of the infant. Moreover, adolescent girls who acquired mpox in pregnancy (and/or their legal guardian) will be asked consent/assent to share additional information related to pregnancy and delivery outcomes.

Signed study consent and assent forms must be kept by the investigator in the Investigator Site File, a copy must be kept in the child's medical record and a copy given to the participant or family.

If the child and/or the parent/legal guardian is illiterate but gives oral assent, a literate witness must sign the consent form instead. Participants who are illiterate should include their thumb print as well.

Participants (or parent/legal guardian of a child) must be informed that participation is voluntary and that they may withdraw from the study at any time, without prejudice. The rights and welfare of the participants will be protected by emphasizing to them that the quality of their medical care will not be adversely affected if they decline to participate in this study.

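### Phase 1 takes one anonymous report when the illness episode ends, leaving no described route for the pregnancy or newborn outcome of an adolescent who is still pregnant then

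*Protocol*

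**What the plan says.** **Phase 1.** Section 2 lists girls infected during pregnancy among the registry's population and outcomes among its data. Section 3.1 (Phase 1 registry) adds, as an option, "pregnancy and neonatal data both for adolescents who are pregnant or up to 28 days postnatal and have mpox". On timing, section 3.1 states: "Data for each patient will be reported at a single point in time, at the end of the clinical episode", with discharge given as an example. Section 5 repeats it: "Summary data will be entered at the end of each patient's clinical episode". Section 6.1 adds: "In Phase 1 data will be fully anonymous therefore no identifiers will be recorded". Section 5 also says that patients already in the Phase 1 database will not be approached for Phase 2.

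**Phase 2.** Section 3.1 has routine visits entered "until the infant, child or adolescent is considered fully discharged from care (outcome visit". Its next sentence provides for follow-up of infants whose adolescent mothers were infected in pregnancy, ending no later than day 28 of life. Section 8.3 asks these adolescents for consent or assent "to share additional information related to pregnancy and delivery outcomes". Objective (d) in section 2.1.2 includes "among mpox patients who are pregnant, describing the infection status of offspring" and, if feasible, an estimate of vertical transmission risk. Sections 3.1 and 6.1 describe mother–infant ID linkage only for infants who themselves have mpox.

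**The concern.** The Phase 1 reporting time is tied to the illness, whereas the pregnancy data need the end of the pregnancy. An adolescent discharged in mid-pregnancy is reported as still pregnant. The protocol describes no second report, no key by which to reopen the record, and no later move into Phase 2.

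Whether an outcome is known then depends on what the outcome is. A loss during the illness falls inside the reporting window. A continuing pregnancy is known only if delivery comes soon after infection. A description of pregnancies with a known outcome would therefore not describe adolescents with mpox in pregnancy as a whole. Phase 1 carries weight here because Phase 2 is conditional on case numbers and other surveillance, and patients who decline Phase 2 are entered in Phase 1 instead.

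**Working it through.** The protocol states no figure on this point, so there is none to reproduce.

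**Step 1: does another Phase 1 route capture the outcome?** Under section 4.1, a newborn with laboratory-confirmed mpox enters in its own right, and for diagnosis at 28 days or less maternal pregnancy and delivery data are collected. Pregnancy losses and uninfected newborns generate no such record. The infant's record covers infected newborns only, and without identifiers it cannot be joined to an earlier report on the mother.

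**Step 2: how many outcomes would be known?** All inputs are assumptions; none is in the protocol.

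- Diagnosis is spread evenly over gestation, from week 0, 20 or 30 to week 40 (span S = 40, 20 or 10 weeks).
- The report is filed L = 2, 4, 6 or 8 weeks after diagnosis.
- Share delivered by the report = L / S.
- Adding adolescents diagnosed in the 4 weeks after delivery, at the same weekly rate, for S = 40: (L + 4) / 44.
- Share with newborn status known to day 28, for S = 40: max(0, L − 4) / 40.

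| L (weeks) | Weeks 0–40 | Weeks 20–40 | Weeks 30–40 | Weeks 0–40 plus postnatal | Day-28 status known (weeks 0–40) |
|---|---|---|---|---|---|
| 2 | 2/40 = 5% | 2/20 = 10% | 2/10 = 20% | 6/44 = 14% | 0% |
| 4 | 4/40 = 10% | 4/20 = 20% | 4/10 = 40% | 8/44 = 18% | 0% |
| 6 | 6/40 = 15% | 6/20 = 30% | 6/10 = 60% | 10/44 = 23% | 2/40 = 5% |
| 8 | 8/40 = 20% | 8/20 = 40% | 8/10 = 80% | 12/44 = 27% | 4/40 = 10% |

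For even timing over 40 weeks, the median gap from report to term is 20 − L, or 18 to 12 weeks. Historic cases are outside this calculation; many of those pregnancies will have ended before the data are entered.

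**Step 3: direction of the distortion.** Let p be the share of pregnancies lost during the illness and d the share of the rest delivered by the report. Among known outcomes, losses make up p / (p + (1 − p)d). This exceeds p whenever d is below 1. The direction for incident cases follows from the reporting rule; the size depends on p and d, and the protocol gives neither.

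**Step 4: Phase 2.** Infant follow-up to day 28 presupposes that the study learns of the birth. The preceding sentence ends entry at the adolescent's discharge, and nothing says how her record stays open in between. Offspring without mpox do not meet section 4.1 and are not covered by the described linkage, yet they belong in the denominator of a transmission risk.

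**The case against.** The strongest reply is that no Phase 1 objective asks for the outcome of every pregnancy. Section 2.1.1(d) concerns infants with vertically acquired infection, who enter through their own records. The section 7.3 count of congenital infections is likewise made from infected infants. Pregnancy data are optional in Phase 1, and fuller data under consent are what Phase 2 is for. This stands as far as it goes: those items do not depend on when the mother's report is filed. It does not explain what the registry can do with pregnancy data on an adolescent reported before her pregnancy has ended.

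Second, discharge is only an example of when the episode ends. A site that took the episode to run until obstetric discharge would lose nothing. That is true, but the protocol does not say so, and leaving it to each site works against harmonised collection.

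Third, keeping an anonymous form open for months would strain the anonymity on which ethics waivers rest. This is a fair objection to reopening records. It does not apply to submitting the one report later.

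A reader might also infer that Phase 2 loses these outcomes, or that the Phase 1 rule defeats objective 2.1.2(d). The documents do not support either. Section 3.1 provides infant follow-up to day 28, section 8.3 seeks consent for pregnancy and delivery outcomes, section 5 allows linkage to routine records with additional consent, and objective 2.1.2(d) belongs to Phase 2 alone.

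**Conclusion.** The point holds for incident Phase 1 cases still pregnant when reported: the protocol describes no route by which their pregnancy or newborn outcome is recorded. Known outcomes will over-represent losses during the illness and infections near delivery.

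The size is illustrative. If diagnosis is even over 40 weeks and the report follows within 2 to 8 weeks, 80% to 95% of these pregnancies have no delivery outcome at the report. If diagnosis falls only in the last 10 weeks, the figure is 20% to 80%, so a general statement that most outcomes are missing is not secure. Nor do the documents support a figure for an inflated loss proportion: they give no loss rate and do not plan that estimate.

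For Phase 2 the finding is narrower. Two adjacent sentences in section 3.1 are not reconciled, and the route for uninfected offspring is not described. This is worth correcting because the remedy is cheap and widens what the registry can validly describe.

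**What to change.** - **Sections 3.1 and 5, Phase 1.** For any patient pregnant at diagnosis, have the site submit its single anonymous report once the pregnancy has ended and the newborn's status is known from routine records, or at the data cut if that is earlier. A report filed at the cut is marked 'pregnancy ongoing/outcome not known' and left out of the denominators for pregnancy and infant outcomes. Name the cut that applies, since a single report cannot be updated afterwards.
- **Section 3.1, Phase 2.** State that the mother's record stays open until the pregnancy outcome has been entered, whatever the date of her discharge from mpox care.
- **Sections 3.1 and 6.1, Phase 2.** Extend mother–infant linkage to offspring without mpox.

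The cost is protocol wording and an eCRF completion rule, with no added visits and routine data only. A few records arrive later: at most about 40 + 4 = 44 weeks after an infection at the start of pregnancy, or about ten months. Against roughly 18 months of data collection (section 3.2), some outcomes may still be unknown at the final analysis.

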### 2.1 PRIMARY OBJECTIVES

#### 2.1.1 Phase 1 registry

- To describe anonymised data on paediatric and adolescent patients with mpox infection to inform approaches to infection control and prevention during this and future outbreaks, depending on case trajectories, with flexibility to adapt to other (re-) emerging infections in the future. Depending on the numbers reported, this may include:
  - a. monitoring the temporal and geographical distribution of mpox infection in the paediatric and adolescent population, including in specific paediatric/adolescent groups, such as those with underlying conditions or with vertically acquired mpox;
  - b. describing the epidemiology and clinical presentation of the infection/ disease, including outcomes of treatment administered as part of routine care;
  - c. describing the populations at highest risk of severe outcomes, including identifying factors associated with severe disease and death;
  - d. describing characteristics and outcomes of infants with vertically acquired mpox infection.

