### 4.1 INCLUSION CRITERIA

For the Phase 1 registry all infants, children and adolescents aged <18 years at the time of mpox diagnosis, with laboratory-confirmed mpox infection, as per national guidelines, will be eligible for inclusion in the anonymised dataset. Moreover, mothers of eligible infants who are diagnosed with mpox at 28days or less are included in the study to collect maternal data on pregnancy and delivery..

For the Phase 2 observational study all patients meeting the inclusion criteria for Phase 1 will be eligible for inclusion. Patients and their legal guardians will be required to give informed consent/ assent.

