### **7.2 SAMPLE SIZE**

In Phase 1, the preliminary analysis will be largely descriptive. Therefore, no formal sample size calculation has been undertaken, and instead all available data on cases will be utilised. Future specific analyses in Phases 1 and 2 will be assessed for feasibility based on the numbers of cases reported and their characteristics (e.g. numbers with and without a particular exposure of interest, such as age or vaccination).

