### **7.3 ANALYSIS PLAN**

Analysis of the data collected in Phases 1 and 2 will be primarily descriptive, including summaries of:

- Age, sex/ gender, temporal and geographical distribution of children and adolescents with laboratory-confirmed mpox infection
- Description of clinical symptoms, including number of lesions
- Frequency of specified outcomes, including proportion hospitalised and admitted to ICU
- Likely mode of mpox acquisition
- Treatments administered, including use of tecovirimat, its duration and outcomes following treatment
- Number of infants with congenital infections, and description of maternal and infant characteristics

If numbers allow, additional analyses will assess the association between patient characteristics / interventions and outcomes, for example comparing the odds of severe outcomes between patients who did and did not receive specific antiviral treatments or who were versus were not vaccinated, using multivariable logistic regression.

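### Phase 1 takes historic cases with no look-back limit and no check that past cases are complete, so severity proportions and the case curve can partly reflect which past cases were entered

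*Protocol*

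**What the plan says.** Section 3.1 (Phase 1 registry) opens the registry to the past: "Data will be collected on historic cases (occurring before the inception of the registry"). It also takes current cases, "and on incident cases where relevant approvals and/or consent have not been obtained for Phase 2". Section 5 repeats this: "This will include retrospective entry of cases seen before activation of the data entry system as well as incident cases".

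The criteria in 4.1 concern age and laboratory confirmation: "For the Phase 1 registry all infants, children and adolescents aged <18 years at the time of mpox diagnosis, with laboratory-confirmed mpox infection". They contain no calendar limit. The period of about 18 months in section 3.2 describes data collection, not a window for diagnosis.

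Cases arrive by a link shared through clinical networks, "with an invitation to enter details on all cases of mpox infection aged <18 years seen in their centres". On the analysis set, 7.2 says that "instead all available data on cases will be utilised". Section 7.3 lists "Frequency of specified outcomes, including proportion hospitalised and admitted to ICU" together with the distribution of cases over time and place. Objective (a) in 2.1.1 is "monitoring the temporal and geographical distribution of mpox infection in the paediatric and adolescent population".

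**The concern.** The main Phase 1 outputs are proportions among the cases that sites chose, or were able, to enter. For past cases the look-back has no common start, and the protocol does not say how a site is to establish that it has found them all. A site that enters a few well-remembered children from earlier years cannot be told apart from one that enters every laboratory-confirmed case. If children who were admitted or had complications are easier to retrieve, the proportions hospitalised and admitted to ICU come out too high.

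The time pattern is exposed even without selection by severity. If one site searches back ten years and another one year, the case curve partly shows search effort. The same applies to comparisons between settings. Section 1 wants to capture differences by location, income and endemic status, and says that paediatric mpox has historically occurred in endemic regions. Endemic sites may therefore have a much longer past to search.

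Later repair is hard. Under 3.1 and 6.1, Phase 1 records are anonymous and reported once, at the end of the episode. Section 3.1 describes dates of events as additional data collected in Phase 2.

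**Working it through.** The protocol states no severity rate, historic share or completeness figure, so there is no figure to reproduce. What follows is an illustration in which every input is an assumption.

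**Inputs**
- p = true severe proportion, the same in historic and incident cases: 10%
- h = true share of cases that are historic: 50%
- r1 = probability that a severe historic case is entered: 0.9
- r0 = probability that a non-severe historic case is entered: r1 divided by the entry ratio
- incident cases are all entered

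**Formula**

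Observed severe proportion = S / (S + N), where S = h·p·r1 + (1−h)·p and N = h·(1−p)·r0 + (1−h)·(1−p).

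**Results for p = 10%, h = 50%**

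S = 0.5×0.1×0.9 + 0.5×0.1 = 0.095 in each case.
- Ratio 1 (r0 = 0.90): N = 0.405 + 0.45 = 0.855; 0.095/0.950 = 10.0%. No bias.
- Ratio 2 (r0 = 0.45): N = 0.2025 + 0.45 = 0.6525; 0.095/0.7475 = 12.7%.
- Ratio 3 (r0 = 0.30): N = 0.135 + 0.45 = 0.585; 0.095/0.680 = 14.0%.

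**Sensitivity to the historic share (p = 10%)**

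| Entry ratio | h = 25% | h = 50% | h = 75% |
|---|---|---|---|
| 1 | 10.0% | 10.0% | 10.0% |
| 2 | 11.2% | 12.7% | 14.9% |
| 3 | 11.6% | 14.0% | 17.8% |

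Over the same historic shares and ratios of 1.5 to 3, a true 5% reads 5.4% to 9.3% and a true 20% reads 21.3% to 32.7%.

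**Time distribution**

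With h = 50%, p = 10% and ratio 2, the entered historic cases are 0.5×(0.1×0.9 + 0.9×0.45) = 0.2475 of a total of 0.7475. Historic cases then form 33% of the registry instead of 50%. At ratio 1 they form 0.45/0.95 = 47%. So incomplete entry shifts the time pattern even when the severity proportion is unbiased.

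**Does the protocol contain a check?**

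The logic and consistency checks in 6.1 apply to entered records and cannot reveal a case that was never entered. No section asks for a case log, a count of eligible cases or a statement of the period covered.

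**The case against.** Several counter-arguments have weight.

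- **All cases are asked for.** Section 5 invites every case under 18 and includes past ones. Since 4.1 requires laboratory confirmation, a site could list positives from laboratory records instead of relying on memory. Section 4 covers primary and community care, 8.4 allows monitoring and audit, and 8.5 makes incomplete data a reason to close a site. This lowers the risk. It does not remove it, because none of these provisions fixes the period over which completeness is meant or asks sites to report it.
- **Pooling is inferred.** A reader might take 7.3 to say that historic and incident cases will be summarised only together. It does not say so: it lists summaries and is silent on splitting. A statistical analysis plan, not among the documents reviewed, could stratify. It could not recover a period or completeness date that was never collected.
- **The Phase 1 form is not shown.** It may already hold a calendar period, since temporal distribution is a listed summary, and 6.3 makes entries auditable. The claim that a marker is missing cannot be made. The protocol text simply does not commit to one.
- **Incident cases are not a clean reference.** They too are entered after the episode ends. Once Phase 2 opens, those left in Phase 1 are the ones without Phase 2 approval or consent. A reader might infer that incident cases are complete and should carry the headline figures; the documents do not support that.
- **An open look-back suits a rare disease.** Section 1 says numbers are small and wants to identify changes in epidemiology. This stands, and it argues against an eligibility cut-off.

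A reader might also infer that severity could be doubled. With 20 incident cases at 10% severe and 40 entered historic cases at ratio 3, the pooled figure is (2 + 10)/60 = 20%. But if all severe historic cases were entered, those 40 (10 severe, 30 non-severe) imply 10 + 30×3 = 100 true historic cases, or 100/120 = 83% of all cases. That is an extreme mix for which the protocol gives no support.

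**Conclusion.** The point holds in a limited form. The protocol sets no look-back limit, describes no check that past cases are complete, and uses all available cases for severity and temporal summaries. The proportions hospitalised and admitted to ICU can therefore be too high if severe past cases are more likely to be entered. The case curve and comparisons between settings can partly reflect how far back each site searched.

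Neither the presence nor the size of this bias can be established from the protocol. Under the assumptions above, a true 10% would read about 12.7% to 14.0% with half the cases historic, and 11.2% to 17.8% across historic shares of 25% to 75%, for entry ratios of 2 to 3. It would stay at 10% with equal entry. The weakness concerns how the descriptive results can be interpreted and does not undermine the registry itself. It is worth correcting because the information needed has to be collected when each case is entered.

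**What to change.** 1. **Section 5:** ask each site to declare the date from which it has entered all its laboratory-confirmed cases. A site that cannot declare one still contributes to the all-case summary.
2. **Phase 1 form:** make sure it holds a historic/incident marker and a diagnosis period coarse enough to keep the data anonymous.
3. **Section 7.3:** report outcome frequencies and temporal distribution for cases inside the declared complete periods, separately from other historic cases and alongside the all-case summary.

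Do not add an earliest date to 4.1: that would make older cases ineligible in a study with few cases. Do not present incident cases as unselected.

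The marker also needs a clear registry start. Section 3.2 gives Phase 1 start as project month 12 (Oct 2023). Counting November 2021 as month 1, which fits every other dated row of that table, month 12 is October 2022. October 2023 would also fall after the August 2023 interim analysis. The entry should be reconciled.

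Cost: one extra site-level field, and up to two short items on the form if they are not already there. No case is discarded. The separate summaries will have smaller denominators and wider intervals.
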